Neutrophils $< 1.0 \times 10^9/L$, platelets $< 50 \times 10^9/L$, creatinine ≥ 1.5 times the upper limit of normal **or** estimated creatinine clearance $< 50 \text{ mL/min/1.73m}^2$ (Cockcroft-Gault formula), serum aspartate aminotransferase or alanine aminotransferase concentration $> 3 \times \text{ULN}$ or total bilirubin $\geq 1.5 \times \text{ULN}$

Progressive malignancy, uncontrolled infection or any major organ dysfunction as defined by the protocol

Design:

This is a Phase 1/2 trial to determine the safety and efficacy of baricitinib in patients with cGVHD that is refractory to steroids.

Patients will initially be treated with baricitinib at 2mg daily for 12 weeks. If the response at 12 weeks is a CR and there has not been a DLT, the dose will remain at 2mg daily for an additional 12 weeks, with the primary response assessment at 24 weeks of total treatment. If the response is a PR or stable disease, the dose will be increased to 4mg daily for an additional 12 weeks, with the primary response assessment at 24 weeks of total treatment. If there is progression of disease at any time within the first 12 weeks, the dose can be increased to 4mg daily at that time, and patients will continue for a total of 24 weeks of treatment. Patients will have the option to continue baricitinib for an additional 6 months as tolerated if they have stable or responding disease.

The co-primary endpoint of safety will be determined by rate, severity, and duration of adverse events based on CTCAE v4 criteria. Assessment for DLTs will occur every 2 weeks during the first 4 weeks of each dose level. Safety monitoring will occur every 4 weeks thereafter.

The co-primary endpoint of efficacy will be defined as rate of overall response at 24 weeks per NIH consensus criteria (CR or PR).

Peripheral blood samples will be collected prior to treatment, at 2 weeks, at 12 weeks and every 12 weeks thereafter to evaluate cytokine and cellular profiles, STAT phosphorylation, candidate chronic GVHD biomarkers. Pharmacokinetic studies will also be performed at each dose level.

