In an initial futility analysis, if 0 of the first 7 patients enrolled in cohort 1 have responded at 12 weeks, then a 2nd cohort of patients will be accrued to start treatment at the higher dose (4mg daily). Otherwise, if 1 or more of the first 7 patients respond in cohort 1, then 21 evaluable patients will be treated in cohort 1. Similarly, if the second cohort is used, and if 0 of the 7 patients enrolled in this second cohort have responded at 12 weeks, then no further patients will be accrued. Otherwise, if 1 or more of the first 7 patients respond in cohort 2, then 21 evaluable patients will be treated in cohort 2.

A total of 21 evaluable patients will be enrolled in either cohort 1 or 2 as appropriate, in order to have 80% power to detect a response rate consistent with 30% and ruling out 10%, with a one-sided significance level of 0.10 for the cohort. As an early stopping rule for safety, if 2/3 or greater patients at any given dose level experiences a dose limiting toxicity requiring dose reduction or discontinuation, that dose will not be subsequently used and no further dose escalation will take place.

TABLE OF CONTENTS

PRÉCIS	2
TABLE OF CONTENTS	4
STATEMENT OF COMPLIANCE	7
1 INTRODUCTION	7
1.1 Study Objectives	7
1.2 Background and Rationale	7
2 ELIGIBILITY ASSESSMENT AND ENROLLMENT	12
2.1 Eligibility Criteria	12
2.2 Screening Evaluation	14
2.3 Participant Registration and Status Update Procedures	14
2.4 Baseline Evaluation	15
3 STUDY IMPLEMENTATION	16
3.1 Study Design	16
3.2 Drug Administration	19
3.3 Dose Modifications	19
3.4 Questionnaires	20
3.5 Follow-up	20
3.6 Telehealth	21
3.7 Study Calendar	22
3.8 Cost and Compensation	26
3.9 Criteria for Removal from Protocol Therapy and Off Study Criteria	26
4 CONCOMITANT MEDICATIONS/MEASURES	27
4.1 Concomitant Corticosteroid Therapy and Tapering Guideline	27
4.2 Other Treatments for cGVHD	27
4.3 Other Allowed Concomitant Therapy	28
4.4 Prohibited Concomitant Therapy	28
5 CORRELATIVE STUDIES FOR RESEARCH	28
5.1 Biospecimen Collection	28
5.2 Sample Storage, Tracking and Disposition	30
6 DATA COLLECTION AND EVALUATION	32
6.1 Data Collection	32
6.2 Data sharing plans	33

6.3	Response Criteria.....	33
6.4	Toxicity Criteria.....	36
7	NIH REPORTING REQUIREMENTS/DATA AND SAFETY MONITORING PLAN...36	
7.1	Definitions	36
7.2	OHSRP Office of Compliance and Training.....	36
7.3	NCI Clinical Director Reporting	37
7.4	NIH Required Data and Safety Monitoring Plan.....	37
8	SPONSOR SAFETY REPORTING.....	37

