If no patients among the first 7 achieve a CR or PR on 2mg daily at the 12 week response assessment in the first cohort of patients, the second cohort will be enrolled starting at 4mg daily if no safety issues have arisen, with the same parameters for DLT monitoring. Similarly, if 0 of the first 7 treated in cohort 2 have a response, then no further patients will be treated in cohort 2.

If there is at least one patient with a response in the first 7 patients treated on cohort 2, then 21 evaluable patients will be treated in cohort 2.

Concurrent topical and ancillary treatments for cGVHD are allowed per standards of care and will be recorded (see Section 4). Other systemic immune suppression must stay stable or be tapered (systemic immunosuppression taper should be attempted no earlier than after 4 weeks on study), throughout the treatment with baricitinib (with up to 2 steroid pulses allowed for disease stabilization per Section 4.1).

Patients who discontinue therapy for any reason will be followed for up to 24 months after discontinuing baricitinib as indicated in section 3.5.

Peripheral blood samples will be collected prior to treatment, at 2 weeks, at 12 weeks and every 12 weeks thereafter to evaluate cytokine and cellular profiles, STAT phosphorylation, candidate chronic GVHD biomarkers. Pharmacokinetic studies will also be performed at each dose level on day 1 and after 15 days of treatment (Section 5.1.3).

*If ≥ 1 response in cohort 1, 2nd cohort will use identical schema as cohort 1

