3.1.1 Dose Limiting Toxicity

DLT will be defined as any grade ≥ 3 non-hematologic or grade ≥ 4 hematologic adverse event, or hemoglobin < 6.5 g/dL, within 4 weeks of starting any dose level (1mg, 2mg or 4mg) except those that are clearly and incontrovertibly due to extraneous causes. One inpatient dose de-escalation after a DLT will be permitted in patients who have not experienced cGVHD progression. In patients that have experienced disease progression, further dosing will cease in a patient at the occurrence of the first DLT.

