10 STATISTICAL CONSIDERATIONS

The primary objectives of the study are to determine the tolerability and efficacy of baricitinib in patients with steroid-refractory cGVHD. The primary efficacy objective is to treat a total of 21 patients in either cohort 1 or cohort 2 in order to have 80% power to detect a response rate consistent with 30% and ruling out 10%, with a one-sided significance level of 0.10.

Patients will first be enrolled onto cohort 1, and in an initial futility analysis, if 0 of the first 7 patients enrolled in cohort 1 have responded, then subsequent patients will be accrued to cohort 2, starting treatment at the higher dose (4mg daily). If 1 or more of the initial 7 patients treated in cohort 1 has a response, then a total of 21 evaluable patients will be treated in cohort 1.

If patients are enrolled onto cohort 2, and if 0 of the first 7 patients enrolled in cohort 2 have responded, then no further patients will be accrued onto the trial. On the other hand, if 1 or more of the initial 7 evaluable patients enrolled in cohort 2 have responded then a total of 21 evaluable patients will be treated in cohort 2.

As an early stopping rule for safety, if 2/3 or greater patients at any given dose level experiences a dose limiting toxicity requiring dose reduction or discontinuation, that dose will not be subsequently used. Accrual will continue at a lower dose level with no further dose escalation, unless this occurs at the lowest dose level, at which time accrual to the study will be stopped.

If patients are enrolled in both cohort 1 and cohort 2, then up to 28 evaluable patients may be required (either 21 in cohort 1 or 7 in cohort 1 and 21 in cohort 2). In order to allow for a small number of inevaluable patients, the accrual ceiling will be set at 31. It is anticipated that 8-12 patients may be enrolled onto this protocol per year; thus, 2 to 4 years may be required to accrue up to 31 patients.

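### The two-thirds DLT closing rule has no minimum number, look schedule or denominator, and its Section 10 fallback can send patients back to 2 mg after 0/7 responses there

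*Combined protocol and SAP*

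**What the plan says.** The rule appears in the Précis, in 3.1.1.1 and in Section 10. A dose is closed "if 2/3 or greater patients at any given dose level experiences a dose limiting toxicity requiring dose reduction or discontinuation". The Précis adds that "that dose will not be subsequently used and no further dose escalation will take place". Section 10 goes further: "Accrual will continue at a lower dose level with no further dose escalation, unless this occurs at the lowest dose level", in which case accrual to the study stops.

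No statement of the rule gives a number of patients, a time to apply it or a stopping probability. Nearby text sets the frequency of patient-level assessment ("Assessment for DLTs will occur every 2 weeks during the first 4 weeks of each dose level", Précis). Section 7.4.1 has the team meet weekly and base dose-level decisions on toxicity in prior patients. Neither passage mentions the two-thirds rule.

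The dose levels are 1, 2 and 4 mg (3.1.1.1), and the 4-week DLT window restarts at each level (3.1.1). Cohort 1 patients with a partial response or unchanged disease at week 12 move to 4 mg (3.1). Cohort 2 starts at 4 mg and opens on this condition: "If no patients among the first 7 achieve a CR or PR on 2mg daily at the 12 week response assessment". In that event "the second cohort will be enrolled starting at 4mg daily if no safety issues have arisen".

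**The concern.** Safety is a co-primary endpoint, and this is the only numeric rule for closing a dose level. Three things are left open.

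- **When the rule first applies.** After 2 DLTs in the first 3 patients, a team that looks from n=3 closes the dose, while a team that looks from n=7 treats four more patients first. With no minimum, 1 of 1 closes a dose, yet 13 of 21 (62%) does not.
- **Who is counted.** The denominator is the dose level, so escalated cohort 1 patients presumably count at 4 mg, but the text does not say so. Nor does it say whether patients still inside the 4-week window count.
- **What follows a closure.** Cohort 2 exists only because none of seven patients responded on 2 mg. If 4 mg then closes, the next level down is 2 mg, with no escalation allowed, so the safety fallback contradicts the futility decision. If 2 mg closes in cohort 1, accrual moves to 1 mg, which has no cohort or arm in 2.3.1 and no stated place in the 21-patient efficacy test.

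**Working it through.** The plan gives no operating characteristic for this rule, so there is no figure of its own to reproduce. It also gives no DLT rate; the rates below are assumptions, shown as a range.

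**1. Boundary.** A fraction of at least two-thirds at n patients means DLTs ≥ ceil(2n/3): 2 of 3, 3 of 4, 4 of 5 or 6, 5 of 7, and so on to 14 of 20 or 21.

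**2. Chance of firing by 21 patients.** Exact binomial recursion, one look after each patient from the stated first look. The horizon of 21 is the cohort size in Section 10. These are cumulative probabilities, not single looks.

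| First look | 10% DLT | 20% | 30% | 40% |
|---|---|---|---|---|
| n=1 (literal) | 10.9% | 23.4% | 37.3% | 52.5% |
| n=3 | 2.8% | 10.7% | 23.1% | 39.5% |
| n=4 | 0.4% | 3.4% | 11.3% | 25.8% |
| n=5 or 6 | 0.1% | 1.8% | 7.7% | 20.8% |
| n=7 | 0.02% | 0.6% | 4.0% | 14.2% |

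Starting at n=2 gives the same values as n=3, because 2 DLTs in 2 patients already guarantee at least 2 of 3.

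Hand check at n=3 with a 40% rate: 3 × 0.4² × 0.6 + 0.4³ = 0.288 + 0.064 = 0.352. So 35.2 of the 39.5 points arise by the third patient. If the rule has not fired by then, the chance over the next 18 patients is (0.3949 − 0.352)/(1 − 0.352) = 6.6%.

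**3. Return to 2 mg.** Let m be the number of the first seven cohort 1 patients who escalate and are pooled at 4 mg, and c the number of cohort 2 patients (7 or 21). With looks from n=3, equal DLT risk in both groups, and DLT independent of response:

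P(path) = P(0/7 responses) × [P(fire by m+c) − P(fire by m)].

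The first factor is 0.9⁷ = 0.478 at a 10% response rate and 0.7⁷ = 0.082 at 30% (the two rates in Section 10). This counts only closures after cohort 2 patients begin to add to the 4 mg total. At a 40% DLT rate:

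| m pooled | 10% response | 30% response |
|---|---|---|
| 0-2 (0 = not pooled) | 18-19% | 3.1-3.3% |
| 3-5 | 1.7-2.1% | 0.3-0.4% |
| 6-7 | 0.6-0.7% | 0.1% |

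Example with m=7, c=21 at 10% response: 0.478 × (0.3952 − 0.3796) = 0.0075, or 0.74% with unrounded inputs. At a 10% DLT rate and 10% response, the path is 1.4% with m=0 and below 0.001% with m=7.

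**The case against.** The strongest reply is that the rule is clear enough in practice. The wording can be read as 2 of 3 patients, which puts the first look at n=3 and removes most of the spread. The label of an early stopping rule, the two-weekly DLT assessments and the weekly team meeting all point to near-continuous review. The 40% DLT rate comes from no document, and the protocol describes a good safety profile at 0.5-20 mg, mainly in other diseases. At a 10% rate the contrast is 0.02% against 2.8%.

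Much of this stands. The 2-of-3 reading is plausible, but the text does not state it, and the denominator would still be undefined. The dependence on the first look does not rest on the 40% rate: the ratio between n=7 and n=3 is larger at the lower rates.

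On the fallback, the reply is stronger. After 0/7 responses, patients with unchanged disease go to 4 mg and those who progress may do so, so most of the seven should reach that level. The dose-level definitions favour pooling them, which puts the path below 1% even at a 40% DLT rate. Cohort 2 also opens only if no safety issues have arisen, and 0 of 7 in cohort 2 ends accrual. These limits make the path rare, but neither expressly bars the return to 2 mg once cohort 2 is open and 4 mg has closed.

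A reader might infer that patients are unprotected. The documents do not support that: the patient-level DLT and dose-modification rules in 3.1, 3.1.1 and 3.3, the weekly review in 7.4.1 and the suspension clause in 13.1 operate however the two-thirds rule is read.

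**Conclusion.** The point holds as a minor gap in pre-specification. The closing rule is not reproducible as written: the unstated first look changes its chance of firing by 21 patients from 14.2% (n=7) to 39.5% (n=3) at an assumed 40% DLT rate, and from 0.6% to 10.7% at 20%. No DLT rate that ought to close a dose is stated, so these figures show dependence on the first look; they do not show that the rule is too strict or too lax.

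The fallback is a direct conflict between two stated rules, but on a rare path: about 0.6-0.7% at a 40% DLT rate and 10% response rate with six or seven escalated patients pooled. A reader might take the 18-19% figure as the expected risk. It requires that at most two of the seven be counted at 4 mg, which is not the natural reading of a dose-level denominator. All figures assume independent patients with a constant DLT rate, each assessed before the next is counted.

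**What to change.** In the Précis, 3.1.1.1 and Section 10:

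1. State that if 4 mg closes after cohort 1 has met 0/7, accrual stops and does not revert to 2 mg.
2. Apply the rule from exactly 3 patients, firing when DLTs requiring dose reduction or discontinuation reach ceil(2n/3). Let n count every patient at that dose level, including escalated cohort 1 patients and once per level, who has had such a DLT or completed the 4-week window. If the first two patients both have such a DLT, close the dose at once, since closure at n=3 is then certain. Report the stopping probabilities by 21 patients: 2.8 / 10.7 / 23.1 / 39.5% at DLT rates of 10 / 20 / 30 / 40%.
3. State that if 2 mg closes in cohort 1, patients accrued at 1 mg are reported descriptively, outside the 21-patient efficacy test, up to a number the sponsor sets.

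The cost is a few sentences and a small calculation, with no new data. The two-thirds fraction and the type of DLT counted stay as they are. There are three downsides. A dose no longer closes on 1 of 1. The trial may end earlier on the rare path in (1). Pooling slows later firing at 4 mg: with a 40% DLT rate, if seven pooled patients have not triggered the rule, the chance over the next 21 is (0.3952 − 0.3796)/(1 − 0.3796) = 2.5%.

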11 COLLABORATIVE AGREEMENTS

11.1 COOPERATIVE RESEARCH AND DEVELOPMENT AGREEMENT (CRADA)

Baricitinib is provided by Eli Lilly and Company under a CRADA (# 34604).

12 HUMAN SUBJECTS PROTECTIONS

12.1 RATIONALE FOR SUBJECT SELECTION

No subjects will be excluded from participation based on gender, race or ethnicity. The study will be open to all subjects who satisfy the inclusion criteria and provide an informed consent to the protocol.

12.2 PARTICIPATION OF CHILDREN

As there is inadequate published data on baricitinib in children, this study will be limited to subjects age 18 years or older.

12.3 PARTICIPATION OF NIH SUBJECTS UNABLE TO GIVE CONSENT

Adults unable to give consent are excluded from enrolling in the protocol. However, re-consent may be necessary and there is a possibility, though unlikely, that subjects could become decisionally impaired. For this reason and because there is a prospect of direct benefit from research participation (section 12.5), all subjects will be offered the opportunity to fill in their wishes for research and care, and assign a substitute decision maker on the “NIH Advance Directive for Health Care and Medical Research Participation” form so that another person can make decisions about their medical care in the event that they become incapacitated or cognitively impaired during the course of the study. Note: The PI or AI will contact the NIH Ability to Consent Assessment Team (ACAT) to assess ongoing capacity of the subjects and to identify an LAR, as needed.

Please see section 12.6.1 for consent procedure.

12.4 EVALUATION OF BENEFITS AND RISKS/DISCOMFORTS

12.4.1 Related to baricitinib

Potential risks of baricitinib include the range of toxicities described in Section 14.1.2 and the consent form. There may also be unexpected side effects. All subjects will be carefully monitored for side effects.

12.4.2 Related to Blood Collection

Minor complications including bleeding, pain, and hematoma formation at the site of blood draws, or infections may rarely occur.

12.4.3 Related to Tissue Biopsy

Skin and oral punch biopsy is a minor surgical procedure that may be associated with temporary bleeding, hematoma at the site, local infection and postoperative discomfort. These risks are small (generally <5%) and transient.

12.4.4 Related to Pulmonary Function Tests

PFTs are safe for most participants; however, some may experience dizziness, shortness of breath and fainting. In rare PFTs may lead to a collapsed lung. In participants with asthma, PFTs may precipitate an asthma attack.

12.4.5 Related to ECG and echocardiogram

Other than possibly experiencing some minor skin irritation from the electrodes there are no anticipated risks related to complete the electrocardiogram and/or the echocardiogram.

12.4.6 Related to Questionnaires

The potential risk of questionnaires include questions that may be sensitive in nature.

12.4.7 Related to Radiation Exposure

A CT scan is done at screening; however, all screening is performed on a separate study. Therefore, radiation risks are assessed to the screening protocols.

12.5 RISKS/BENEFITS ANALYSIS

The benefits of the study include the potential to improve knowledge of the biology of cGVHD and impact of JAK inhibition in the treatment of this disease. In addition, if shown to be effective, the study drug may improve overall outcomes after SCT, a curative therapy for many hematologic malignancies, as well as have implications for prevention. Individual patients may benefit from participation in this protocol if treatment stabilizes or improves their cGVHD. Patients may also benefit by knowing they are participating in a study aimed at improving treatment of cGVHD, which we ultimately hope will benefit future patients. The risks of the study to participants are minimal compared to the potential benefits to them or to the overall knowledge and future study of JAK inhibition in cGVHD.

12.6 CONSENT PROCESS AND DOCUMENTATION

The informed consent document will be provided as a physical or electronic document to the participant or consent designee(s) as applicable for review prior to consenting. A designated study investigator will carefully explain the procedures and tests involved in this study, and the associated risks, discomforts and benefits. In order to minimize potential coercion, as much time as is needed to review the document will be given, including an opportunity to discuss it with friends, family members and/or other advisors, and to ask questions of any designated study investigator. A signed informed consent document will be obtained prior to entry onto the study.

The initial consent process as well as re-consent, when required, may take place in person or remotely (e.g., via telephone or other NIH approved remote platforms used in compliance with policy, including HRPP Policy 303) per discretion of the designated study investigator and with the agreement of the participant/consent designee. Whether in person or remote, the privacy of the subject will be maintained. Consenting investigators (and participant/consent designee, when in person) will be located in a private area (e.g., clinic consult room). When consent is conducted remotely, the participant/consent designee will be informed of the private nature of the discussion and will be encouraged to relocate to a more private setting if needed.

Consent will be documented with required signatures on the physical document (which includes the printout of an electronic document sent to participant) or as described below, with a manual

(non-electronic) signature on the electronic document. When required, witness signature will be obtained similarly as described for the investigator and participant.

Manual (non-electronic) signature on electronic document:

When a manual signature on an electronic document is used for the documentation of consent at the NIH Clinical Center, this study will use the following to obtain the required signatures:

- Adobe platform (which is not 21 CFR Part 11 compliant); or,
- iMedConsent platform (which is 21 CFR Part 11 compliant)

During the consent process, participants and investigators will view individual copies of the approved consent document on screens at their respective locations (if remote consent); the same screen may be used when in the same location, but is not required.

Both the investigator and the participant will sign the document using a finger, stylus or mouse.

Note: Refer to the CCR SOP PM-2, Obtaining and Documenting the Informed Consent Process for additional information (e.g., verification of participant identity when obtaining consent remotely) found at:

<https://ccrod.cancer.gov/confluence/pages/viewpage.action?pageId=73203825>.

For the optional biopsy, the patient will consent at the time of the procedure. If the patient refuses the optional biopsy at that time, the refusal will be documented in the medical record and in the research record.

